Table 4	TEAEs in $\geq 2\%$ of subjects in either SB206 treated group or Vehicle group (NI-MC302)	28
Table 5	BOTE Inflammation Score	50
Table 6	Local Skin Reaction Scale	53
Table 7	Study Drug	55
Table 8	Assessment of Causality	61
Table 9	Grading System for Patch Test Reactions (at each time point)	77
Table 10	Challenge Reaction Interpretation (based on the last reading (at least 48 hours after patch removal)	77

LIST OF FIGURES

Figure 1	Study Timeline Diagram	20
Figure 2	NI-MC301: Percentage of Subjects with Complete Clearance	28
Figure 3	NI-MC302: Percentage of Subjects with Complete Clearance	29
Figure 4	Structure of Berdazimer Sodium (active ingredient in SB206)	56

LIST OF APPENDICES

Appendix 1	Procedure for Suspected Sensitization	76
------------	---	----

LIST OF ABBREVIATIONS

Abbreviation	Definition
AD	Atopic Dermatitis
AE	Adverse Event
BID	Twice Daily
BOTE	Beginning-of-the-end
BSA	Body Surface Area
CFR	Code of Federal Regulations
CM	Concomitant Medication
CRO	Clinical Research Organization
CSR	Clinical Study Report
DSMB	Data and Safety Monitoring Board
ECG	Electrocardiogram
e-consent	Electronic Consent
eCRF	Electronic Case Report Form
ET	Early Termination
FDA	Food and Drug Administration
GCP	Good Clinical Practice
GEE	Generalized Estimating Equation
hMAP3	Hydrolyzed N-Methylaminopropyl-trimethoxysilane
IB	Investigator's Brochure
ICF	Informed Consent Form
ICH	International Conference on Harmonisation
IEC	Independent Ethics Committee
IP	Investigational Product
IRB	Institutional Review Board
ITT	Intent-to-Treat
IUD	Intrauterine Device
IUS	Intrauterine Hormone Releasing System
IWRS	Interactive Web Response System

LLOQ	Lower Limit of Quantitation
LSR	Local skin reaction (post exposure to study drug)
MC	Molluscum Contagiosum
MedDRA	Medical Dictionary of Regulatory Affairs
NO	Nitric Oxide
NOVAN	Novan, Inc.
OTC	Over the counter
PK	Pharmacokinetic
PP	Per-Protocol Population
QD	Once daily
SAE	Serious Adverse Event
SAF	Safety Population
SAP	Statistical Analysis Plan
SD	Standard Deviation
SOA	Schedule of Assessments
SOC	System Organ Class
SOP	Standard Operating Procedure
TEAE	Treatment Emergent Adverse Event
UPT	Urine Pregnancy Test

1 SYNOPSIS

Title	A Phase 3 Multi-Center, Randomized, Double-Blind, Vehicle-Controlled, Parallel Group Study Comparing the Efficacy and Safety of SB206 and Vehicle Gel Once Daily in the Treatment of Molluscum Contagiosum
Short Title	A Phase 3 Molluscum Contagiosum Efficacy and Safety Study
Acronym	B-SIMPLE4
Phase	3
Study Design	
This is a phase 3 multi-center, randomized, double-blind, vehicle-controlled, parallel group study to be conducted in up to approximately 850 subjects 6 months of age and older with molluscum contagiosum (MC). After obtaining informed consent/assent, subjects who satisfy entry criteria will be randomized 1:1 (active:vehicle). Subjects receiving current treatment for MC at the time of the Screening Visit will enter a wash out period of up to 14 days prior to randomization. In the event no wash out period is required, Screening and Baseline visit activities may be combined into a single visit. At randomization, subjects will be stratified by investigator type (dermatologist vs. other), the subject's BOTE score at Baseline (no inflammation (BOTE = 0) vs. mild/moderate/severe inflammation (BOTE ≥ 1) and number of randomized subjects per household (1 subject per household vs. 2 subjects per household). Subjects will be stratified to 5 strata first by subjects per household. Subjects from 1 subject households will be stratified by investigator type and baseline BOTE score. Subjects from 2 subject households will not be further stratified with respect to investigator type and baseline BOTE score because the overall sample size that is expected for the stratum for households with two subjects is not large enough to support further stratification.
 
The sponsor, investigator, site staff and study subjects will remain blinded to the study treatment during this study. All treatments are dosed topically, once daily (QD). Each dose will consist of berdazimer gel or vehicle gel that will be mixed with hydrogel on a supplied dosing guide, and then immediately applied by the subject to the affected designated area(s).

	
Subjects or their caregivers will apply treatment once daily to all lesions identified at Baseline and new lesions that arise during treatment for a minimum of 4 weeks and shall continue unless otherwise instructed by the investigator up to 12 weeks. If the investigator determines all lesions are cleared at a visit, the investigator may instruct the subject to stop treatment. If treatment is stopped due to clearance, subjects will continue regularly scheduled visits through Week 24/ET2. Study drug will be dispensed through Week 12/ET1 in case of lesion recurrence between study visits. At each visit subsequent to stopping treatment due to clearance, the investigator will determine if new lesions have occurred since the last visit, and if so, the subject or caregiver will be instructed by the investigator to re-initiate treatment. If the subject or caregiver see new lesions or re-occurrence of lesions in between visits, they should treat these lesions until the next visit. No study drug is planned to be provided after the Week 12 visit.
 
The subject or caregiver will apply study drug to the individual lesions. Periocular lesions will be treated if the lesions are at least 2 cm from the edge of the eye.
 
Subjects will visit the clinic in person at Screening/Baseline, Week 2, Week 4 (unless visit is performed remotely), Week 8, Week 12, and Week 24. At Baseline, the investigator will perform in person lesion counts. Then, the subjects/caregivers will be instructed on how to participate in remote visits and practice the technology. Once the initial in person lesion count has been completed by the assessor, an additional count by the same investigator will be made utilizing the remote technology platform to serve as a training for future remote visit.
 
Subjects will be contacted via phone on Day 2 to collect subject information on early dose reactions. The Week 4 Visit may be performed remotely or as an in-clinic visit. At Weeks 16 and 20, subjects will be contacted via phone to capture information regarding MC recurrence and adverse events (AEs); at Week 24, the subject will be seen at the site for a final study visit to assess scarring, keloids, and MC recurrence. Subjects who discontinue the study prior to the Week 12 visit due to AEs or other reasons will be asked to complete the Week 12 visit assessments; this will

--	--

	
be recorded as an Early Termination (ET1) visit. Subjects who discontinue from the study after Week 12 but prior to Week 24 will be asked to come to the site to complete Week 24 assessments; this visit will be recorded as an ET2 visit.
 
Safety assessments include Beginning of the End (BOTE) Inflammation Scores, Local Skin Reactions (LSRs), adverse event collection, including presence of scars/keloids, and urine pregnancy tests (UPTs). Safety assessments except UPTs will be completed at all visits through Week 12; UPTs will be completed at Screening, Baseline, and Week 12. After Week 12, safety information for ongoing and new AEs will be collected, along with information regarding household MC occurrence.
 
Additional procedures include subject/caregiver completion of a the Global Severity Assessment and the Global Impression of Change Assessment by the investigator and the subject/caregiver at Week 12 and 24. These procedures are designed to provide insight into the subject/caregiver’s experience with MC and current MC disease state. A select number of sites will also consent subjects/caregivers to participate in a study exit interview, to be arranged by a third party after completion of Week 12. The interview will include questions to further detail the subject/caregiver perspective of their MC and treatment experience.

Target Population	Males and females, 6 months of age and older, with a minimum of 3 and a maximum of 70 MC lesions at Baseline
Number of Subjects	Approximately 850 Subjects will be assigned 1:1 to active:vehicle.
Length of Participation	On treatment: Approximately 12 weeks Safety follow-up period: Approximately 12 weeks In study (including screening and safety follow-up): Up to approximately 26 weeks

Intervention	
SB206 10.3% or Vehicle Gel once daily
 
Inflammatory reactions around the MC have been associated with imminent resolution of MC (sometimes referred to as “beginning-of-the-end” [“BOTE”] sign). In most cases, clinical features can differentiate between BOTE and LSR. BOTE may be associated with itch, but not pain. BOTE is usually asymptomatic, self-limited, localized to individual MC lesions, and does not require discontinuation of study treatment or additional treatment. LSR is generally more diffuse, associated with significant itch or tenderness, may necessitate discontinuation of study treatment, and may need treatment for symptomatic relief (e.g. a topical corticosteroid or topical anesthetic). For very severe LSR, systemic corticosteroids may be considered. Investigators will assess the treatment area at each scheduled visit and use their medical judgement to differentiate between BOTE and LSRs. The subject’s baseline skin inflammatory condition will be assessed as part of the physical examination to be completed prior to randomization. BOTE Inflammation Score and LSR scores will be recorded at each visit. LSRs will be rated on individual features including erythema, flaking/scaling, crusting, swelling, vesiculation/pustulation, and erosion/ulceration. When LSRs are clinically significant, the investigator should report the condition as AE(s).
 
Clinically significant LSRs that are reported as adverse events and/or subject reported intolerability (i.e. itching, pain) may result in an investigator directed temporary treatment hold (drug holiday), and topical corticosteroids may be used to treat LSRs for up to 2 weeks. Per the investigator’s instructions, the subject may re-initiate study drug treatment prior to the next scheduled visit. Upon re-initiation (challenge) of study drug treatment, if a subject develops worsening LSRs, allergic contact dermatitis may be suspected. In the event of suspected allergic contact dermatitis, photographs may be taken of the affected area(s) and transmitted to the contract research organization (CRO) medical monitor for review and confirmation of allergic contact dermatitis prior to initiating patch testing. Consent must be in place for patch testing to occur. The investigator should also discuss the necessity of patch testing with the subject/caregiver. The investigator will then

---------------------	---

[figure not shown]
	
discontinue the subject from study drug treatment and treat the area(s) with corticosteroids for up to 2 weeks. If the subject provides consent/assent, the investigator will consult the CRO medical monitor prior to implementing the process for patch testing.
 
Adverse events will be assessed and collected after the initiation of study drug treatment through the end of the subject’s last visit. Treatment related adverse events will be followed up until resolution or up to one year after last treatment, whichever is sooner.
 
The investigator will map locations of the molluscum lesions at Baseline in clinic and through the remote visit platform. The investigator will count and record the number of active (raised, treatable) molluscum lesions per body area. Additional lesions identified through Week 12 will be mapped at each visit. Using the map as a guidance, the investigator will assess the treated areas for scar/keloid formation. Scar formation will be assessed starting at the Week 4 visit through Week 12 and again at Week 24. Scars will be considered an adverse event for the purposes of this study. In addition, treatment related keloid/hypertrophic scars will also be recorded as adverse events.
 
If a subject’s treatment is discontinued by the investigator or the subject because of an AE, that AE should be indicated as the reason for treatment discontinuation. All subjects will be encouraged to remain in the study throughout the 24-week study duration, even if treatment is discontinued prematurely.

Primary Endpoint
	
This study is being conducted to evaluate the efficacy and safety of SB206 10.3% QD for the treatment of MC. The primary endpoint will evaluate the proportion of subjects with complete clearance of all treatable MC at Week 12.

Secondary Endpoints
	
 • Proportion of subjects achieving a lesion count of 0 or 1 of all treatable MC at Week 12 • Proportion of subjects achieving at least a 90% reduction from Baseline in the number of all treatable MC at Week 12 • Proportion of subjects with complete clearance of all treatable MC at Week 8 • Percent change from Baseline in the number of all treatable MC at Week 4

Safety Endpoints	
 • Incidence of treatment-emergent adverse events • Change from Baseline in LSR scores • Change from Baseline in abbreviated physical examinations • Concomitant medications reported • Proportion of subject(s) with reported scar(s)
Other Endpoint	
 • Change from Baseline in BOTE scores
Exploratory Endpoints	
 • Percent change from Baseline in number of treatable MC at Weeks 2, 8, and 12 • Proportion of subjects achieving a lesion count of 0 or 1 of all treatable MC at Weeks 2, 4, and 8 • Proportion of subjects achieving at least a 90% reduction from Baseline in the number of all treatable MC at Weeks 2, 4 and 8 • Proportion of subjects achieving at least a 75% reduction from Baseline in the number of all treatable MC at Weeks 2, 4, 8 and 12 • Absolute change from Baseline in number of treatable MC at Weeks 2, 4, 8 and 12 • Proportion of subjects with complete clearance of all treatable MC at Weeks 2 and 4 • Time to complete clearance of all treatable MC • Proportion of subjects who have a recurrence of MC after the first visit at which complete clearance was observed • Subject-reported spread to household members as measured by any new occurrence of MC in household members of subjects at Weeks 2, 4, 8, 12 • Investigator Global Severity Assessment at Baseline, Week 12 and 24 • Subject Global Severity Assessment at Baseline, Week 12 and 24 • Investigator Global Impression of Change at Week 12 and 24 • Subject Global Impression of Change at Week 12 and 24
Number of Sites	Approximately 55 sites in the United States
Study Duration	
Estimated start date: 01 Sep 2020
 
Projected stop date: 31 Mar 2021
 
Estimated duration: 3.5 months of enrollment

1.1 Study Schematic

The study schematic is presented in [Figure 1](#).

Figure 1 Study Timeline Diagram

*Subjects that do not require a washout may have Screening and Baseline procedures conducting on the same day. Screening/Baseline visits will be done in-clinic if completed on the same day.

*Week 12 procedures should be completed for subjects who early terminate (ET) from the study prior to Week 12; Week 24 procedures should be completed for subjects who ET after Week 12 but prior to Week 24.

1.2 Schedule of Assessments

The schedule of assessments (SOA) is presented in [Table 1](#).

Table 1 Schedule of Assessments

	Screening	Treatment					
	Screening ¹ (Day -15 to Day 1)	Visit 1 ¹ Baseline (Day 1)	Visit 2 TC (Day 2)	Visit 3 ² Week 2 (Day 15 ±3)	Visit 4 ² Week 4 (Day 29 ±5)	Visit 5 ² Week 8 (Day 57 ±5)	Visit 6 ² Week 12/ ET1 (Day 85 ±5)
Informed Consent (Assent)	X						
Demographics	X						
Medical and Medication History	X						
Molluscum Lesion Count	X	X ³		X	X	X	X
Physical Exam ⁴		X					X
Urine Pregnancy Test ⁵	X ⁶	X					X
BOTE Inflammation Score ⁷		X (pre-dose)		X	X	X	X
Local Skin Reactions (LSR) ⁸		X (post-dose)		X	X	X	X
Scarring/Keloid Assessment					X	X	X
Review of Inclusion/Exclusion Criteria	X	X					
Drug Dispensed		X			X	X	
Collect Study Drug					X	X	X
Provide instructions on and test remote visit technology		X					
Provide Subject Diary		X					
Review Subject Application Instructions		X		X	X	X	
In Clinic Study Drug Application ⁹		X		X	X	X	X
Review/reinforce Study Drug Compliance				X	X	X	X
Record Adverse Event (AE) and Concomitant Medication (CM) Changes		X	X	X	X	X	X
Household status of MC ¹⁰	X	X		X	X	X	X
Investigator Global Severity Assessment & Subject Global Severity Assessment		X					X
Investigator Global Impression of Change & Subject Global Impression of Change							X
Consent for Study Exit Interview ¹¹		X					

	Safety Follow-up		
	Visit 7 Week 16 TC (Day 113 ± 7 days)	Visit 8 Week 20 TC (Day 141 ± 7 days)	Visit 9 Week 24/ET2 (Day 169 ± 7 days)
Scarring/Keloid Assessment			X
Record Adverse Event (AE) and Concomitant Medications ¹⁰	X	X	X
Household status of MC ¹⁰	X	X	X
Investigator Global Severity Assessment & Subject Global Severity Assessment			X
Investigator Global Impression of Change & Subject Global Impression of Change			X

¹ Screening and Baseline may occur on the same day. If this occurs, lesion count and review of inclusion/exclusion criteria will only occur once.
 
² All visit dates are in reference to Baseline (e.g. Week 2 occurs 14 days after Baseline Visit). The Week 4 visit may be performed remotely or in clinic. Baseline, Week 2, Week 8, Week 12, and 24 visits will be performed in clinic. Day 2, Week 16, and Week 20 will be performed via phone. If a subject terminates early, an in-clinic visit is preferred, but a remote visit may be performed with sponsor approval.
 
³ Lesion counts will be performed twice during the Baseline visit; the first assessment will be performed by the investigator in person, and the second assessment will be performed by the investigator through image evaluation.
 
⁵ The physical exam will include a directed examination of the skin (presence or absence of individual features of erythema, flaking/scaling, crusting, swelling, vesiculation/pustulation, and erosion/ulceration).
 
⁶ Females who have reached 9 years of age, unless they are post-menopausal (at least 12 months of continuous amenorrhea without an alternative medical cause), or surgically sterilized (documented hysterectomy, documented bilateral salpingectomy, or documented bilateral oophorectomy). Tubal ligation does not meet the definition of surgically sterile.
 
⁷ UPT will be performed at Screening if the visit takes place in the clinic.
 
⁸ BOTE Inflammation Score will be assessed pre-dose at Baseline. The Baseline LSR assessment should be done at least 30 minutes after study drug is applied on Day 1. After Baseline, BOTE Inflammation score and LSRs can be evaluated at any time pre- or post-dose during the visit, regardless of whether lesions are present and whether study drug is applied.
 
⁹ Study drug application will occur in clinic at Baseline, Week 2, Week 4, Week 8, and Week 12. On days when a remote visit will occur, subjects/caregivers will not apply the study drug until the study visit so that the mixing/application of study drug can be observed by site staff during the remote visit.
 
¹⁰ At Screening, subjects should be asked if any household members currently have MC. In addition to recording AE and CM changes, subjects should be asked if there are any new occurrences of MC in household members of subjects at each visit, except Day 2.
 
¹¹ Follow up interviews will be performed with selected consented subjects that complete Week 12. Consent can be obtained starting at Baseline, and the follow up interview will be performed with the subject/caregiver at a later date.
 
NOTE: The Week 4 visit can be performed in clinic or remote. Baseline, Week 2, Week 8, Week 12, and Week 24 should be performed in clinic wherever possible. Day 2, Week 16, Week 20 should be performed as telephone contacts. Unscheduled visits are permitted as needed for medical reasons. In-clinic unscheduled visits should be reserved for evaluation of adverse events, lesion clearance, and study drug dispensation as needed. Remote unscheduled visits may be utilized as well as/if applicable.
			

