2.1.4.2 Clinical Safety

It should be noted some subjects have experienced transient asymptomatic erythema at the application site within 5 minutes of dosing, which typically lasted ≤ 15 minutes. This is due to nitric oxide's vasodilatory pharmacologic effect and is an expected event.

Summaries of the safety analyses of the phase 3 studies ([NI-MC301](#) and [302](#)) are ongoing, and the CSRs are under preparation. The treatment emergent adverse event (TEAE) profile of SB206 through the Week 24 was found to be favorable and was very similar between the two studies. Study drug discontinuations in the SB206 treatment arm were all due to application site reactions and no treatment-related serious adverse events were reported across both studies.

Table 2 Overall Summary of TEAEs (Safety Population) through Week 24

	NI-MC301		NI-MC302	
	Vehicle (n=116)	SB206 (n=235)	Vehicle (n=117)	SB206 (n=237)
Subjects who reported at least one TEAE	36 (31.0%)	115 (48.9%)	30 (25.6%)	120 (50.6%)
Serious TEAE	0	0	1 (0.9%)	1 (0.4%)
Treatment-related TEAE	19 (16.4%)	86 (36.6%)	8 (6.8%)	86 (36.3%)
TEAE leading to study drug discontinuation	1 (0.9%)	7 (3.0%)	1 (0.9%)	17 (7.2%)

The TEAEs reported in greater than 5% of subjects in the SB206 treated groups were application site pain and application site erythema, with the majority of these TEAEs being mild or moderate in severity.

Table 3 TEAEs in $\geq 2\%$ of subjects in either SB206 treated group or Vehicle group (NI-MC301)

	Vehicle (n=116)			SB206 (n=235)		
	Mild	Moderate	Severe	Mild	Moderate	Severe
Application site pain	8 (6.9%)	0	0	34 (14.5%)	16 (6.8%)	1 (0.4%)
Application site erythema	2 (1.7%)	1 (0.9%)	0	13 (5.5%)	15 (6.4%)	1 (0.4%)
Application site pruritus	0	0	0	8 (3.4%)	2 (0.9%)	1 (0.4%)
Pyrexia	3 (2.6%)	1 (0.9%)	0	7 (3.0%)	4 (1.7%)	0
Application site exfoliation	0	0	0	4 (1.7%)	5 (2.1%)	1 (0.4%)
Application site scar	9 (7.8%)	0	0	6 (2.6%)	0	0
Application site swelling	1 (0.9%)	0	0	5 (2.1%)	1 (0.4%)	0
Application site dermatitis	1 (0.9%)	0	0	1 (0.4%)	3 (1.3%)	1 (0.4%)
Application site discolouration	0	0	0	5 (2.1%)	0	0
Vomiting	1 (0.9%)	0	0	2 (0.9%)	5 (2.1%)	0
Upper respiratory tract infection	2 (1.7%)	0	0	3 (1.3%)	2 (0.9%)	0

Table 4 TEAEs in $\geq 2\%$ of subjects in either SB206 treated group or Vehicle group (NI-MC302)

[figure not shown]
	Vehicle (n=117)			SB206 (n=237)		
	mild	moderate	severe	mild	moderate	severe
Application site pain	1 (0.9%)	1 (0.9%)	0	15 (6.3%)	22 (9.3%)	0

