6.4 Remote Visits

Week 4 can be performed as a remote visit or in clinic visit. All subjects/caregivers will be instructed on the technology to be utilized during the Baseline visit. Approximately 24-48 hours in advance of the remote visit, the subject or caregiver should utilize the historic lesion map to

take images of all lesion areas noted at the previous visit and any new lesion areas that developed since the previous visit. Photographs of the lesions should be taken prior to IP application for the day or at least 1 hour after application. The remote visit should be rescheduled within visit window if acceptable images have not been received by the site. Additional instructions on how to take and upload photographs is provided in the Study Reference Manual.

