7.1.2 Other Assessments

7.1.2.1 BOTE Inflammation Score

Inflammatory reactions around MC lesions has been associated with imminent resolution of MC (sometimes referred to as “beginning-of-the-end” [“BOTE”] signs). Investigators should educate subjects and caregivers on the characteristic stages of BOTE as it is recognized as the natural course of self-limiting clearance of MC. BOTE may be associated with itching, but not pain. BOTE is usually asymptomatic, self-limited, localized to individual MC lesions, and does not require discontinuation of study treatment or additional treatment.

Investigators will assess the treatment area at each scheduled visit and use their medical judgement to differentiate between BOTE and LSRs. The BOTE Inflammation Score will be recorded at each visit ([Table 5](#)).

Table 5 BOTE Inflammation Score

Score	Global Assessment	Description
0	No inflammation	No evidence of local inflammation
1	Mild	Minimal erythema and/or edema
2	Moderate	Definite erythema and/or edema with or without hemorrhagic crusting
3	Severe	Erythema and edema with definite hemorrhagic crusting
4	Very Severe	Strong reaction spreading beyond the treated area, bullous reaction, erosions

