8.6 Assessment and Verification of Compliance

Subjects will be provided a diary to record doses taken on a daily basis. The diary will contain a reminder for subjects to not administer their dose the day of each visit. Review of subject compliance with the diary completion and dosing will be conducted at each visit. Subject compliance will be based on calculation from the missed doses recorded from the subject diary and from additional information noted in the source (e.g. investigator instructed interrupted or modified doses).

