## 12. OTHER ANALYSES

The following analyses of BOTE vs lesion count will be presented:

- Percent change from Baseline in the number of treatable MC at each visit in relation to the Baseline BOTE score comparing No Inflammation vs Inflammation within each treatment group through a repeated measures mixed model with number of randomly assigned subjects in household (1 subject vs 2 subjects), investigator type (dermatologist

vs other), BOTE score at Baseline (no inflammation [BOTE=0] vs mild/moderate/severe/very severe inflammation [BOTE $\geq$ 1]), BOTE score at Baseline by visit interaction, age, and baseline lesion count as covariates with a compound symmetry covariance matrix.

- Percent change from Baseline in the number of treatable MC at Week 12 in relation to the highest post-baseline BOTE score during treatment will be summarized descriptively.
- Percent change from Baseline in the number of treatable MC at Week 12 in relation to the highest BOTE score at any visit (including Baseline) will be summarized descriptively.
- Percent change from Baseline in the number of treatable MC at each visit in relation to the BOTE score at Week 2 will be summarized descriptively.

In these analyses, the BOTE scores will be analyzed in the ITT Population as follows:

1. Dichotomized:
  - a. Score of 0: No Inflammation
  - b. Score of 1, 2, 3, or 4: Mild to Very Severe

A shift table comparing the baseline BOTE score to each scheduled post-baseline assessment will be presented for the ITT Population.

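### After Baseline the BOTE score may be taken minutes after an in-clinic dose, so SB206's expected transient erythema can raise it from 0 to 1; the size is unknown and only descriptive BOTE results are exposed

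*Protocol*

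**What the plan says.** **Timing of BOTE.** Protocol Section 1.2, footnote 8 to the Schedule of Assessments, sets the first score: "BOTE Inflammation Score will be assessed pre-dose at Baseline". For all later visits it says: "After Baseline, BOTE Inflammation score and LSRs can be evaluated at any time pre- or post-dose during the visit". The same footnote gives the Baseline skin-reaction score a minimum wait: "The Baseline LSR assessment should be done at least 30 minutes after study drug is applied on Day 1". Footnote 9 has study drug applied in clinic at Baseline and at Weeks 2, 4, 8 and 12.

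**The drug effect.** Protocol Section 2.1.4.2 reports that "some subjects have experienced transient asymptomatic erythema at the application site within 5 minutes of dosing, which typically lasted ≤ 15 minutes". It attributes this to nitric oxide's vasodilatory action and calls it expected. Section 2.1.5 repeats the point.

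**The scale.** In Protocol Section 7.1.2.1, a BOTE score of 1 is defined as "Minimal erythema and/or edema".

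**Other timing rules.** For remote visits, Protocol Section 6.4 says: "Photographs of the lesions should be taken prior to IP application for the day or at least 1 hour after application". On home dosing, Section 8.6 says: "The diary will contain a reminder for subjects to not administer their dose the day of each visit".

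**Use of the scores.** Change in BOTE from Baseline is the single item in the Other tier of Protocol Section 3. SAP Section 12 plans a shift table and several summaries based on post-baseline BOTE, among them "Percent change from Baseline in the number of treatable MC at Week 12 in relation to the highest post-baseline BOTE score during treatment". For these it splits the score into 0 against 1 to 4.

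**The concern.** BOTE is meant to capture inflammation that heralds natural resolution of the lesions. The Baseline score cannot contain the drug flush because it is taken before any drug is applied. A later score can contain it if it is taken soon after the observed in-clinic dose.

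The flush is attributed to the active ingredient, so the error would fall on SB206 and not, by that mechanism, on vehicle. It would also act exactly at the boundary between 0 and 1 at which the SAP splits the score. More BOTE on SB206 could then be read as the drug hastening natural resolution when part of it was vasodilation. The summary by highest post-baseline score is the most exposed, because one inflated score at any visit is kept.

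Neither document asks for the time of scoring relative to the dose to be recorded, so affected scores could not be picked out afterwards.

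**Working it through.** The plan gives no figure on this point, so there is none to reproduce. The check sets the timing rules side by side and then illustrates the size under stated assumptions.

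**1. Flush window.** Onset is within 5 minutes and typical duration is up to 15 minutes (Protocol Section 2.1.4.2). The flush is then typically over by 5 + 15 = 20 minutes after dosing.

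**2. Does the permitted scoring time overlap that window?**

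| Assessment | Rule | Overlap with 0 to 20 minutes |
|---|---|---|
| BOTE, Baseline | before dosing | none |
| Skin reactions, Baseline | at least 30 minutes after | none |
| Photographs for remote visits | before dosing, or at least 1 hour after | none |
| BOTE, in-clinic visits at Weeks 2 to 12 | before or after dosing, no wait | possible |

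**3. What do the visit lists say?** Protocol Sections 6.7.4 to 6.7.7 give these step numbers:

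| Visit | BOTE | Lesion count | Dose |
|---|---|---|---|
| Week 2 | 1 | 3 | 5 |
| Week 4 | 1 | 3 | 8 |
| Week 8 | 1 | 3 | 8 |
| Week 12 | 2 | 4 | 10, only if lesions are present |

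BOTE always precedes the dose in these lists. No text makes the order binding, and footnote 8 expressly permits the reverse for BOTE.

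**4. Illustration of size.** Let b be the true share of subjects with BOTE of 1 or more (the same in both arms), f the share of SB206 subjects who flush, and w the share of scores taken inside the flush window. Assume no flush on vehicle. The false excess of BOTE of 1 or more on SB206 at one visit is

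excess = (1 − b) × f × w.

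The documents give none of b, f or w; all values below are assumptions.

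| b | f | w | excess |
|---|---|---|---|
| any | any | 0 | 0 |
| 0.4 | 0.1 | 0.1 | 0.6 × 0.1 × 0.1 = 0.6 points |
| 0.2 | 0.1 | 0.25 | 0.8 × 0.1 × 0.25 = 2.0 points |
| 0.4 | 0.3 | 0.25 | 0.6 × 0.3 × 0.25 = 4.5 points |
| 0.2 | 0.5 | 0.5 | 0.8 × 0.5 × 0.5 = 20 points |

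For b from 0.2 to 0.4, and f and w each from 0.1 to 0.5, the range is 0.6 to 20 percentage points. If every site follows the listed order, w is 0 and so is the excess.

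**5. Erythema reported as an adverse event.** Summing the severity columns of Tables 3 and 4 in Protocol Section 2.1.4.2:

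- NI-MC301: SB206 (13 + 15 + 1)/235 = 29/235 = 12.3%; vehicle (2 + 1)/116 = 3/116 = 2.6%.
- NI-MC302: SB206 (10 + 14 + 2)/237 = 26/237 = 11.0%; vehicle 0/117.

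These are adverse-event rates with no durations given, so they do not estimate f. They do show that application-site erythema in general was commoner on SB206.

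**The case against.** The strongest reply is that sites already have an order to follow. BOTE comes first or second at every treatment visit, the dose comes later, and subjects are reminded not to dose at home that day. Contamination needs a site to depart from that sequence and then score within about 20 minutes. Investigators must also use judgement to separate BOTE from skin reactions, and the flush is described to them as transient and expected. Post-baseline BOTE lies outside the test hierarchy and its analyses are descriptive.

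Most of this stands, and it limits the point. It does not remove it, because footnote 8 allows the departure in plain terms. The guidance on judgement (Protocol Sections 4.1, 7.1.2.1 and 7.2.3) contrasts lesion-limited, usually symptomless BOTE with more diffuse, itchy or tender skin reactions. A symptomless flush where gel was put on individual lesions fits the BOTE side of that contrast, and the guidance never mentions the flush.

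A reader might infer four stronger things that the documents do not support:

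- **That flushed skin cues the evaluator to the arm just before the primary assessment.** At Week 12 the dose depends on whether lesions are present and is listed after the count. The freedom in footnote 8 covers BOTE and skin reactions, not lesion counts.
- **That BOTE cannot be told apart from the flush at all.** The overlap is confined to scores taken in the short window after dosing.
- **That the events-of-special-interest summary in SAP Section 13.3 is inflated.** It counts moderate BOTE, which is score 2. Nothing shows that the flush reaches that grade.
- **That the 30-minute and 1-hour rules show the sponsor had seen this problem.** Neither rule comes with a reason. For photographs, visible product is another possible one, since the mixed gel is opaque white.

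**Conclusion.** The concern holds in a limited form. As written, the protocol permits a comparison of a flush-free Baseline BOTE with a later score that may include the drug's own erythema, on the SB206 arm and at the 0 to 1 boundary. The results exposed are the change in BOTE from Baseline, the BOTE shift table, and the SAP Section 12 summaries by highest or Week 2 BOTE.

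The size is not known. The 0.6 to 20 points above rest wholly on assumed inputs and should not be quoted as an estimate; the true value may be near zero. The primary endpoint, BOTE as a stratification factor and model covariate, and the one modelled BOTE analysis in SAP Section 12 are not shown to be affected. All of the BOTE terms among these use the pre-dose Baseline score. Sample size and power are untouched. This is a small but real gap in wording that is cheap to close.

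**What to change.** In footnote 8 of Protocol Section 1.2 and in Section 6.6, replace the freedom to score BOTE before or after dosing with a requirement to score it before the in-clinic application. This matches Baseline and the order already listed in Sections 6.7.4 to 6.7.7. If a subject has already dosed that day, score no sooner than 1 hour after application, the limit that Section 6.4 already uses for photographs. Record the time of the BOTE score relative to the dose.

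The cost is a wording change, a time field on the case report form, and a small loss of scheduling flexibility. No extra visit or procedure is needed. The change removes overlap with the typical flush only. Application-site erythema that lasts longer would still have to be separated from BOTE by judgement, and the BOTE results should be read with that in mind.
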